13. DATA COLLECTION – STUDY MONITORING AND AUDIT

The Principal Investigator at each clinical site is responsible for assuring the accuracy and completeness of all study documentation. To assure adequate protection of the rights of human subjects, per 21 CFR §812.40, 812.43 and 812.46, this study will be monitored by the Clinical Coordinating Center (CCC) and the Data Coordinating Center (DCC) at Cincinnati Children's Hospital. Monitoring will be conducted within ICH/GCP Guidelines. Clinical Monitoring Plan to ensure the following:

- The facilities continue to be acceptable.
- The protocol is appropriately followed.
- Any agreed upon changes to the protocol have been approved by the IRB
- Accurate, complete and current records are maintained and available for all patients.
- For each subject, collection of protocol-required data and entry of that data into the CRFs must be completed as soon as reasonably possible following that subject's last day in each study period.
- The information recorded and submitted to the CCC and the DCC is representative of the patient's record and other supporting documentation.
- Accurate, complete and timely adverse event reports for serious adverse events are submitted to the CCC and the DCC.
- The Principal Investigator continues to assume primary responsibility for the study.

The Investigator or designee must, upon request, provide to the CCC and the DCC monitors or FDA Investigator the necessary study records for a thorough review of the study's progress. These records include, but are not limited to, original documents and records, such as hospital and clinic charts, consent forms, and laboratory records. The Principal Investigator is required to notify the Sponsor Investigator immediately of the following:

- Withdrawal of IRB Approval
- Any protocol violations or protocol deviations related to study device use
- Notification that Informed Consent was not obtained or consent was withdrawn
- Any other instance in which the Investigator or Sponsor deems it necessary

Additional visits can be scheduled at the request of the Sponsor-Investigator.

APPENDIX A – PEDIATRIC RISK OF MORTALITY (PRISM II) SCORE [28]

ORGAN SYSTEM	MEASURE
Respiration	PaO ₂ to FiO ₂ Ratio, P _a CO ₂ , Resp. Rate
Coagulation	Protime, PTT
Liver	Serum Total Bilirubin
Cardiovascular	Systolic BP, Diastolic BP, Heart rate
Central nervous system	Glasgow Coma Score, Pupillary Reflexes
Metabolic	Serum potassium, calcium, glucose, bicarbonate glucose

ORGAN SYSTEM	MEASURE	FINDING	POINTS
Respiration	PaO ₂ to FiO ₂ Ratio (please see Pulmonary System Conversion Table for Non-ventilated Pts)	200 – 300 mmHg	2
		<200 mmHg	3
	P _a CO ₂	51-65 mmHg	1
		>65	5
	Respiratory Rate (breath/min)	51-70	1
		>70 or Apnea	5
Coagulation	Protime or Partial Thromboplastin Time	1.5 x control	2
Liver	Serum Total Bilirubin	>3.5 mg/dL	6
Cardiovascular	Systolic Blood Pressure (mmHg)	150-200 or 65-75	2
		>200 or 50-64	6
	Diastolic Blood Pressure (mmHg)	>110	6
	Heart Rate (beat/min)	>150 or <80	4
Central Nervous System	Glasgow Coma Score	<8	6
	Pupillary Reactions	Unequal or dilated	4
		Fixed and dilated	10
Metabolic	Potassium (mEq/L)	3.0 – 3.5 or 6.5 – 7.5	1
		<3.0 or >7.5	5
	Calcium (mg/dL)	7.0 – 8.0	2
		12.0 – 15.0 or <7.0	6
	Glucose (mg/dL)	40-60 or 250 – 400	8
		<40 or >400	8
	Bicarbonate (mEq/L)	<16 or >32	3

Conventions used for the above table include:

- PaO₂ is in mmHg and FiO₂ in percent from 0.21 to 1.00.

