Study Endpoints	
In this Pilot study four domains of interest have been designated. The four domains are:
 
 • Patient Safety: Safety Endpoint Measures include adverse events, laboratory safety parameters, vital signs, EKG, ventilation status and hemodynamic variables. • Clinical Efficacy: The Primary Clinical Efficacy Endpoint Measure is in-hospital; 28 and 60-day all-cause mortality. Time to renal recovery and necessity for chronic dialysis up to day 60 will also be determined. Additional efficacy endpoints include time to intensive care unit (ICU) discharge, and time to hospital discharge. • Device Integrity and Performance: The Endpoint Measure is SCD use without failure. This measure will help assess the integrity and performance of the SCD device. • SCD Mode of Action: Exploratory Endpoint Measures will include inflammatory cytokines, cell activation parameters and biomarkers at clinical sites with this capability. The analysis will be performed at a central laboratory.
Assessment of Device Integrity and Performance	
Criteria for assessment of device integrity and performance include:
 
 • Significant Clotting within the Device as assessed by visual inspection. • Evidence of leakage (i.e., cracking/breakage of a port, connector, hemofilter cartridge or tubing).

	
 Any unforeseen malfunction that results in the need for discontinuation.
Study Populations	Pediatric patients with a body weight (BW) between ≥ 10 and ≤ 20 kg receiving care in the Intensive Care Units of each participating hospital will be screened daily and identified for participation in the trial.
Study Design	This is an open-label, multi-center Pilot study.
Approximate Number of Subjects	Up to 10 patients will be enrolled in this study.
Approximate Number of Centers	Up to 7 Clinical Centers in the United States will participate in this study.
Duration of Subject Participation	Each patient will be followed for 60 days following enrollment.

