- Evidence of leakage (i.e., cracking/breakage of a port, connector, hemofilter cartridge or tubing).
- Any unforeseen malfunction that results in the need for discontinuation.

This trial is an early safety efficacy study but is not powered for statistical significance. Insights into a comparison of historical controls matched to SCD treated subjects will utilize the ppCRRT Registry to match for: etiology of AKI, co-morbidities, CRRT modality, dose and form of anticoagulant, adverse events. [10]

The ppCRRT Registry has data fields for the primary reason for CRRT, including AKI and its cause, as well as co-morbidities which will be matched for primary organ system involvement. The CRRT modality was evenly distributed between convective and diffusive modality, with 60% of the convective modalities provided as CVVH and 40% as CVVHDF. The anticoagulant protocol will be standardized with ACD-A/CaCl₂ and all centers

used the same protocol in ppCRRT Registry as outlined in this study protocol. Thus, the ppCRRT Registry dataset will be able to be matched to our study subject cohort. Also as noted above, subjects will be matched for age, size and PRISM II score.

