Besides the test of the hypothesis the study is focused on observable, empirical and laboratory determinations of subject safety while on the SCD. Previous human trials have been conducted on the SCD device and the protocol contains a review of AE and SAE data from all SCD human studies and findings from those studies contributed to constructing the investigative safety profile. Safety endpoint measures specified in the protocol include adverse events, laboratory safety parameters, vital signs, ventilation status and hemodynamic variables. Device integrity and performance measurements are also defined as are circumstances which demand premature termination of SCD treatment.

Prolonged exposure to the SCD is anticipated to result in superior outcomes, although as noted above, this pilot study is not designed to assess for efficacy. However, we understand that a minimum amount of exposure to the SCD will be required for an appropriate safety analysis and for making any inference regarding efficacy. The ppCRRT experience demonstrated that the majority of patients (201/370) received CRRT for 1 to 7 days and exhibited 65% survival (Symons et al CJASN 2007 Table7).

This trial is an early safety efficacy study but is not powered for statistical significance. Insights into a comparison of historical controls matched to SCD treated subjects will utilize the ppCRRT Registry to match for: etiology of AKI, co-morbidities, CRRT modality, dose and form of anticoagulant, adverse events. [10]

The ppCRRT Registry has data fields for the primary reason for CRRT, including AKI and its cause, as well as co-morbidities which will be matched for primary organ system involvement. The CRRT modality was evenly distributed between convective and diffusive modality, with 60% of the convective modalities provided as CVVH and 40% as CVVHDF. The anticoagulant protocol will be standardized with ACD-A/CaCl₂ and all centers used the same protocol in ppCRRT Registry as outlined in this study protocol. Thus, the ppCRRT Registry dataset will be able to be matched to our study subject cohort. Also as noted above, subjects will be matched for age, size and PRISM II score.

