APPENDIX A (Continued)
PEDIATRIC RISK OF MORTALITY (PRISM II) SCORE [28]

GLASGOW COMA SCORE

The Glasgow Coma Score (GCS) is scored between 3 and 15, 3 being the worst and 15 the best. It is composed of the three parameters listed below:

Best Eye Response (4)

1. No eye opening
2. Eye opening to pain
3. Eye opening to verbal command
4. Eyes open spontaneously

Best Verbal Response (5)

1. No verbal response
2. Incomprehensible sounds
3. Inappropriate words
4. Confused
5. Oriented

Best Motor Response (6)

1. No motor response
2. Extension to pain
3. Flexion to pain
4. Withdrawal from pain
5. Localizing pain
6. Obeys commands

A Coma Score of 13 or higher correlates with a mild brain injury, 9 to 12 is a moderate injury and 8 or less a severe brain injury.

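### Appendix A's PRISM II table, a matching variable for the registry comparison, has a glucose split with no effect, missing extreme bands for systolic pressure and calcium, and conflicting FiO2 rules

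*Combined protocol and SAP*

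**What the plan says.** Section 3.2 of the combined protocol and SAP states that "subjects will be matched for age, size and PRISM II score". Section 12 repeats it: "Also as noted above, subjects will be matched for age, size and PRISM II score". Neither gives a tolerance, a ratio or an algorithm. PRISM II is absent from the longer list of ppCRRT control factors later in Section 12. Section 3.1 places the comparison with historic mortality and dialysis data inside the primary objective.

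Appendix A gives the scoring table. On the items at issue:

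- **Glucose (mg/dL):** "40-60 or 250 – 400" scores 8; below 40 or above 400 also scores 8.
- **Systolic pressure (mmHg):** 150-200 or 65-75 scores 2; above 200 or 50-64 scores 6. Nothing is given below 50.
- **Calcium (mg/dL):** 7.0-8.0 scores 2; "12.0 – 15.0 or <7.0" scores 6. Nothing is given above 15.0.
- **FiO2 convention:** "PaO₂ is in mmHg and FiO₂ in percent from 0.21 to 1.00". The pulmonary conversion table lists FiO2 under a percent heading, from 24 to 99+.
- **Simple oxygen mask:** 5-6 L/min gives 40%, 6-7 gives 50% and 7-8 gives 60%.

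The documents do not say how PRISM II was scored in the registry.

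**The concern.** A severity score used for matching must give the same points for the same physiology in both groups, and more points for worse physiology. The printed table does not guarantee either. Two of its rules allow two answers for one child, two let a worse value score less, and one draws a distinction that changes nothing.

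What is at stake is which registry child becomes the control. With up to 10 treated children and 1:1 matching (my assumption, since no ratio is stated), a changed outcome in one control moves control mortality by 1/10, or 10 percentage points. The smaller the cohort, the more each mis-score matters to the descriptive result.

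**Working it through.** No sample-size or power figure bears on this, so there is nothing of that kind to reproduce. The check applies the Appendix A rules exactly as printed.

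**1. Gradient across graded items** (less extreme / more extreme points)

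| Item | Points | Step |
|---|---|---|
| PaO2/FiO2 | 2 / 3 | 1 |
| PaCO2 | 1 / 5 | 4 |
| Respiratory rate | 1 / 5 | 4 |
| Systolic pressure | 2 / 6 | 4 |
| Potassium | 1 / 5 | 4 |
| Calcium | 2 / 6 | 4 |
| Pupils | 4 / 10 | 6 |
| Glucose | 8 / 8 | 0 |

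Glucose of 35, 50, 300 and 401 mg/dL all score 8, and 61-249 scores 0. If the less extreme band was meant to carry anything from 0 to 8 points (assumption), the over-score is 8 minus that value, so 0 to 8. If it was meant to follow the steps of the other items (a narrower assumption), the over-score is 1 to 6. For scale, the highest total as printed is 3+5+5+2+6+6+6+4+6+10+5+6+8+3 = 75.

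**2. Missing extreme bands**

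- Systolic 50 scores 6; systolic 49 matches no row, so 0 if read literally.
- Calcium 15.0 scores 6; calcium 15.1 matches no row, so 0 if read literally.

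Each is a drop of 6 points at the worse value.

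**3. FiO2 unit**

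The rule is PaO2/FiO2 below 200 scores 3, 200-300 scores 2, higher scores 0. The conversion table gives saturation 99 as PaO2 145, and 1 L/min by nasal cannula as FiO2 24.

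- As a fraction: 145/0.24 = 604, 0 points.
- As a percentage: 145/24 = 6.0, 3 points.

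The error is 3 points when the correctly computed ratio exceeds 300, 1 point when it is 200-300, and none below 200.

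**4. Overlapping mask bands** (FiO2 as a fraction)

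| Flow | Saturation (PaO2) | Lower-band ratio, points | Upper-band ratio, points |
|---|---|---|---|
| 6 L/min | 96 (86) | 86/0.40 = 215, 2 | 86/0.50 = 172, 3 |
| 6 L/min | 97 (96) | 96/0.40 = 240, 2 | 96/0.50 = 192, 3 |
| 6 L/min | 99 (145) | 145/0.40 = 362, 0 | 145/0.50 = 290, 2 |
| 7 L/min | 98 (112) | 112/0.50 = 224, 2 | 112/0.60 = 187, 3 |

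Both readings are permitted by the printed table, and they differ by 1 or 2 points.

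**The case against.** **The glucose row is not a contradiction.** Every glucose value has exactly one score. That is right: the row is redundant, and a misprinted or misread digit in one cell could explain it. The other three defects do not depend on that cell.

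**Systolic pressure below 50 will seldom occur in trial children.** Section 5.3 excludes a child with systolic below 80 and diastolic below 40 together, so one with systolic below 50 is eligible only if diastolic is at least 40. This largely stands, provided pressure at scoring resembles pressure at screening. But nothing says registry controls pass the same screen, so a registry child at 45 could lose the points even if both groups use this table.

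**The FiO2 slip would be noticed.** The convention gives the numeric range as a fraction, and bands at 200 and 300 make sense only on that scale; with percentages, no tabulated value exceeds 6.0. This is fair for a manual scorer who looks at the ratio. It does not help with the mask overlap, where both answers look plausible.

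**A reader might infer that the errors favour SCD**, because over-scored children are paired with sicker controls. The documents do not support this. The glucose row could over-score, but the systolic and calcium gaps under-score and push the other way if they fall on trial children. Bias from the glucose row also needs the registry to have been scored by different rules, which is not stated; if this table served both groups, that row loses discrimination without creating a difference.

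**A reader might also see a conflict in the coma score**, since points start below 8 while the appendix text calls "8 or less a severe brain injury". That sentence is descriptive and sets no points, so the two can coexist.

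**The stakes are limited.** The plan says "This trial is an early safety efficacy study but is not powered for statistical significance" and "Up to 10 patients will be enrolled in this study", and PRISM II is one of many matching factors. This bounds the damage, but the historical comparison still sits in the primary objective.

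**Conclusion.** The table should not be used for matching as printed. It contains one split with no effect (glucose), two missing extreme bands (systolic pressure and calcium, 6 points each if read literally) and two genuine inconsistencies: the FiO2 unit, worth up to 3 points, and the mask bands, worth 1 or 2 points in children on a simple mask without a blood gas. The glucose error lies between 0 and 8 points if the less extreme band was meant to carry 0 to 8; the documents do not reveal the intended value.

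Mis-scoring relative to the registry is possible but not shown, and its net direction is unknown. The consequence is confined to a descriptive comparison of up to 10 children; adverse-event and device data do not depend on this table. It is worth correcting because the correction is cheap before scoring and may be impossible afterwards if only totals are recorded.

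**What to change.** Before matching:

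1. Check Appendix A line by line against the score it cites. Correct or confirm the glucose points, close the systolic and calcium bands at their extremes, and make the mask flow bands mutually exclusive.
2. State FiO2 as a fraction and instruct scorers to divide the conversion-table percentages by 100.
3. Record the component values where available, not only the total.
4. Confirm that registry scores used the same rules. If they did not, or this cannot be established, rescore both groups with one algorithm where registry components exist; otherwise report the limitation beside the matched results.

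The cost is one appendix page and possibly a few case report form fields: the baseline list in Section 6.4 names the PRISM II score but does not itemise clotting times, respiratory rate, coma score or pupils. Rescoring depends on registry component data, whose availability the documents do not state.

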APPENDIX A (Continued)
PEDIATRIC RISK OF MORTALITY (PRISM II) SCORE [28]

GLASGOW COMA SCORE

The Glasgow Coma Score (GCS) is scored between 3 and 15, 3 being the worst and 15 the best. It is composed of the three parameters listed below:

Best Eye Response (4)

1. No eye opening
2. Eye opening to pain
3. Eye opening to verbal command
4. Eyes open spontaneously

Best Verbal Response (5)

1. No verbal response
2. Incomprehensible sounds
3. Inappropriate words
4. Confused
5. Oriented

Best Motor Response (6)

1. No motor response
2. Extension to pain
3. Flexion to pain
4. Withdrawal from pain
5. Localizing pain
6. Obeys commands

A Coma Score of 13 or higher correlates with a mild brain injury, 9 to 12 is a moderate injury and 8 or less a severe brain injury.

APPENDIX A (Continued)
PEDIATRIC RISK OF MORTALITY (PRISM II) SCORE [28]

PULMONARY SYSTEM CONVERSION TABLE

O₂ Saturation Conversion Table	Conversion Table for FiO₂
Pulse oximetry O ₂ saturation may be used for calculating PaO ₂ /FiO ₂ ratio when ABG not available	When measured on mask or nasal cannula

SaO ₂ (%)	Calculated PaO ₂
80	44
81	45
82	46
83	47
84	49
85	50
86	52
87	53
88	55
89	57
90	60
91	62
92	65
93	69
94	73
95	79
96	86
97	96
98	112
99	145

Nasal Cannula	
100% O ₂ Flow Rate (L/min)	FiO ₂ (%)
1	24
2	28
3	32
4	36
5	40
6	44
Oxygen Mask	
100% O ₂ Flow Rate (L/min)	FiO ₂ (%)
5-6	40
6-7	50
7-8	60
9	90
10	99+
Mask with Reservoir Bag	
100% O ₂ Flow Rate (L/min)	FiO ₂ (%)
6	60
7	70
8	80

APPENDIX B – CRRT MANAGEMENT

Continuous Renal Replacement will be provided to all subjects enrolled in the SCD-PED-02 Trial using automated equipment with integrated ultrafiltration control.

CRRT Modality:	Continuous
Blood Flow Rate:	Prescribed by Investigator Team – Treating Team
Dialysate Type:	Prescribed by Investigator Team – Treating Team
Dialysate Rate:	Prescribed by Investigator Team – Treating Team
Replacement Fluid Type:	Prescribed by Investigator Team – Treating Team
Ultrafiltration:	Prescribed by Investigator Team – Treating Team
Anticoagulation:	Regional Citrate Anticoagulation
Anticoagulation Prescription:	Prescribed by Investigator Team – Treating Team
CRRT Device	Baxter PrismaFlex or PrisMax
Hemofilter:*	Baxter Prismaflex HF 1000 or HF20
CRRT System Change:	Per participating center protocol
SCD [REDACTED] Change:	Every 24 hours \pm 4 hours and as needed
SCD Blood Tubing Set Change	[REDACTED] with each SCD change

*Hemofilters can be provided to site by sponsor upon request. The clinical site will agree to use one of the protocol approved hemofilters for therapy.

APPENDIX C – CRITICAL MEDICATION LIST

The following is a list of medication categories (with examples) to be acknowledged (yes/no) in the Case Report Forms if administered to the patient during the SCD-PED-02 Clinical Trial (starting at 24 hours prior to SCD Treatment until 240 hours of treatment or ICU discharge, whichever comes first). In addition, antibacterial use is captured during the Post SCD follow-up period.

ANTIBACTERIALS FOR SYSTEMIC USE

- Ampicillin
- Azithromycin
- Aztreonam
- Bactrim (Trimethoprim/ Sulfamethoxazole)
- Cefadroxil
- Cefalexin
- Cefazolin
- Cefazolin sodium
- Cefepime
- Cefepime hydrochloride
- Cefoxitin
- Ceftazidime
- Ciprofloxacin
- Ciprofloxacin hydrochloride
- Clindamycin
- Daptomycin
- Doripenem
- Erythromycin
- Gentamicin
- Levofloxacin
- Linezolid
- Meropenem
- Metronidazole
- Moxifloxacin
- Nafcillin
- Piperacillin
- Piperacillin-tazobactam
- Synercid (Quinupristin/ Dalfopristin)
- Tigecycline
- Tobramycin
- Vancomycin

ANTIMYCOTICS FOR SYSTEMIC USE

- Amphotericin B liposome
- Caspofungin
- Fluconazole
- Micafungin

ANTITHROMBOTIC AGENTS

- Acetylsalicylic acid
- Argatroban
- Bivalirudin
- Clopidogrel
- Drotrecogin alfa
- Enoxaparin
- Enoxaparin sodium
- Heparin
- Warfarin sodium

APPENDIX D –REGIONAL CITRATE ANTICOAGULATION (RCA) PROTOCOL EXAMPLE

1. **Purpose:** The purpose of the guidelines is to standardize, to the extent possible, the provision of regional citrate anticoagulation to patients who require CRRT. While these guidelines should govern the CRRT prescription provided to most patients, there will be special circumstances (e.g. inborn errors of metabolism, exogenous toxin removal) that will require deviation from these guidelines.
2. **Regional citrate anticoagulation:** All CRRT circuits will receive regional citrate anticoagulation. The initial prescription and calcium level monitoring will be based on the size of patients and the presence, or lack thereof, of significant hepatic dysfunction. **REMEMBER TO ACCOUNT FOR THESE FLUIDS IN THE PATIENT REMOVAL RATE AS THESE ARE EXTERNAL TO THE CRRT MACHINE.**
 - a. **Patients > 1 year of age and with normal hepatic function:**
 - i. Order ACD-A™ and CaCl₂ (8 grams/1 liter NS) to bedside
 - ii. Initial ACD-A™ rate = 1.5 x CRRT blood pump rate x min/hour (e.g., if blood pump rate is 100 ml/minute; the ACD-A™ rate is 150 ml/hour). This is to be infused at a stopcock or y-connector on access line.
 - iii. Initial CaCl₂ rate = 0.6 x blood pump rate x min/hour (e.g., if blood pump rate is 100 ml/minute; the CaCl₂ rate is 60 ml/hour).
 - iv. Calcium monitoring schedule
 1. Check patient total and ionized calcium prior to CRRT initiation.
 2. Check patient and system ionized calcium 5 minutes after CRRT settings at prescribed rates.
 3. Check patient and system ionized calcium 1 hours after CRRT settings at prescribed rates.
 4. Check patient and system ionized calcium every 6 hours thereafter
 5. Check patient total calcium daily
 6. Check patient and system ionized calcium one hour after any change in ACD-A™ or CaCl₂ rate
 - b. **Desired Calcium Concentration ranges**
 - i. Circuit ionized calcium = 0.25 to <0.40 mmol/L
 - ii. Patient ionized calcium = 1.1 to 1.3 mmol/L (a higher level may be requested by ICU/CICU service if clinically indicated)
 - iii. Patient systemic calcium = 8 to 12 mg/dL
 - c. **Citrate anticoagulation management**

- i. Bedside RN to call for patient ionCa < 1 mmol/L or >1.5 mmol/L, or circuit ionCa < 0.25 mmol/L or \geq 0.40 mmol/L
- ii. Circuit ionCa managed with ACD-A™ rate
 1. For circuit ionCa < 0.25 mmol/L, decrease ACD-A™ 10%
 2. For circuit ionCa \geq 0.40 mmol/L, increase ACD-A™ 10%
- iii. Patient ionCa managed by CaCl₂ rate
 1. For patient ionCa < 0.9, increase CaCl₂ 20%
 2. For patient ionCa 0.9- 1, increase CaCl₂ 10%
 3. For patient ion Ca 1.3-1.5, decrease CaCl₂ 10%
 4. For patient ion Ca> 1.5, decrease CaCl₂ 20%

CITRATE ANTICOAGULATION

Each participating clinical site will use their regional citrate anticoagulation protocol. The clinical site is responsible to achieve and maintain a serum post filter ionized calcium level of <0.40 mmol/L throughout the entire SCD treatment period (day and night). The serum post filter ionized calcium level will be collected from the CRRT Circuit post SCD [REDACTED]. Examples of regional citrate anticoagulation protocols are included in Appendix D. If the site has difficulty in maintaining post-filter iCa levels <0.4mM from prior experience with patients in this body weight between 10 and 20 kg body weight, the Sponsor and Lead Investigator will discuss options of citrate protocols to be used in enrolled patients to meet post filter iCa levels <0.4 mM as required during SCD treatment.

If centers are unable to achieve desired targets, the below fixed flow ratios ensure greater than 75% citrate removal. The recommended calcium infusion rates restore total Ca and systemic iCa to normal. The use of low blood flows (QB <80 ml/min) on the Prismaflex or PrisMax yields low return pressure alarms. These alarms are mitigated with a 5-inch long, small diameter extension tubing between the catheter and the CRRT blood circuit return end. Recommended filter is HF20.

Table 1. FIXED FLOW RATIO (FFR) CRRT-RCA Settings

Settings Weight	Blood QB ml/mi n R=1	Citrate ACDA ml/hour R=1:3	Dialysat e QD mL/hour R=1:30	Post- Dilution QRF mL/hour R=1:10	81.6 CaCl ₂ in D5/0.9%NS mL/hour R=1:1	Effluent QEPP mL/hour R=1:45
10-20 kg	21	63	630	210	21	≥945

The initial Ca infusion rate is the product of blood flow multiplied by a correction factor based on systemic Hb and albumin for optimized precision **Table 2**. The most common correction factors indicated in blue.

Table 2.: Finding the Initial 81.6 mM CaCl₂-infusion rate (ml/h): QB x Correction Factor (Alb, Hb):

Alb Hb	0.0- 0.7 g/dL	0.8- 1.2 g/dL	1.3- 1.7 g/dL	1.8- 2.2 g/dL	2.3- 2.7 g/dL	2.8- 3.2 g/dL	3.3- 3.7 g/dL	3.8- 4.2 g/dL	4.3- 4.7 g/dL	4.8- 5.2 g/dL	5.3- 5.7 g/dL
5-5.9 g/dL	0.97	1	1.04	1.08	1.12	1.15	1.19	1.23	1.26	1.3	1.34
6-6.9 g/dL	0.93	0.97	1.01	1.04	1.08	1.12	1.15	1.19	1.22	1.26	1.3
7-7.9 g/dL	0.9	0.93	0.97	1.01	1.04	1.08	1.11	1.15	1.18	1.22	1.26
8-8.9 g/dL	0.86	0.9	0.93	0.97	1	1.04	1.07	1.11	1.14	1.18	1.21
9-9.9 g/dL	0.83	0.86	0.89	0.93	0.96	1	1.03	1.07	1.1	1.13	1.17

10-10.9 g/dL	0.79	0.82	0.86	0.89	0.92	0.96	0.99	1.02	1.05	1.09	1.12
11-11.9 g/dL	0.75	0.78	0.82	0.85	0.88	0.91	0.94	0.98	1.01	1.04	1.07
12-12.9 g/dL	0.73	0.76	0.79	0.82	0.85	0.88	0.91	0.94	0.97	1	1.03
13-13.9 g/dL	0.69	0.72	0.75	0.78	0.8	0.83	0.86	0.89	0.92	0.95	0.98
14-14.9 g/dL	0.65	0.68	0.71	0.73	0.76	0.79	0.82	0.84	0.87	0.9	0.93
15-15.9 g/dL	0.61	0.64	0.66	0.69	0.72	0.74	0.77	0.8	0.82	0.85	0.88
16-16.9 g/dL	0.57	0.6	0.62	0.65	0.67	0.7	0.72	0.75	0.78	0.8	0.83
17-17.9 g/dL	0.53	0.56	0.58	0.61	0.63	0.65	0.68	0.7	0.73	0.75	0.78
18-18.9 g/dL	0.5	0.52	0.54	0.57	0.59	0.61	0.63	0.66	0.68	0.7	0.73
19-19.9 g/dL	0.46	0.48	0.5	0.53	0.55	0.57	0.59	0.61	0.63	0.65	0.68

Adjust the Ca-infusion rate +/-10-20% using systemic iCa levels every 6 hours:

It is expected that the systemic iCa will usually be near GOAL +/-0.1 mM with the initial Ca infusion rate. Some patients may sequester Ca in their tissues (for instance with acute pancreatitis or rhabdomyolysis) or conversely may release Ca from their bones (for instance with hypercalcemia of malignancy). Systemic citrate accumulation to maximum 1.5-2 mM is also possible in severe shock/liver failure. Such patients may require +10-20% adjustments to their initial Ca-infusion rate based on systemic iCa levels as in Table 3. Systemic iCa >1 mM will be achieved with total Ca \leq 12 mg/dL with the above settings even in severe liver failure.

Table 3: 81.6 mM CaCl₂ Infusion Rate Change Based on Systemic iCa Every 6 hours:

	The patient's ionized calcium level checked every 6 hours: GOAL 1.15 mM				
	Less than <0.95 mmol/L	0.95 – 1.04 mmol/L	1.05 - 1.25 mmol/L	1.26 – 1.4 mmol/L	More than >1.4 mmol/L
Current Ca-infusion Flow Rate mL/h	Increase Rate +20%; notify ICU physician	Increase Rate +10%	No Change	Reduce Rate -10%	Reduce Rate -20%; notify ICU physician
<12	+2 ml/h	+1 ml/h	No change	-1 ml/h	-2 ml/h
12-<17	+3 ml/h	+1.5 ml/h	No change	-1.5 ml/h	-3 ml/h
17-<22	+4 ml/h	+2 ml/h	No change	-2 ml/h	-4 ml/h
22-<27	+5 ml/h	+2.5 ml/h	No change	-2.5 ml/h	-5 ml/h
27-<32	+6 ml/h	+3 ml/h	No change	-3 ml/h	-6 ml/h
32-<37	+7 ml/h	+3.5 ml/h	No change	-3.5 ml/h	-7 ml/h
37-<42	+8 ml/h	+4 ml/h	No change	-4 ml/h	-8 ml/h
42-<47	+9 ml/h	+4.5 ml/h	No change	-4.5 ml/h	-9 ml/h

47-<52	+10 ml/h	+5 ml/h	No change	-5 ml/h	-10 ml/h
52-<57	+11 ml/h	+5.5 ml/h	No change	-5.5 ml/h	-11 ml/h
57-<62	+12 ml/h	+6 ml/h	No change	-6 ml/h	-12 ml/h
62-<67	+13 ml/h	+6.5 ml/h	No change	-6.5 ml/h	-13 ml/h
67-<72	+14 ml/h	+7 ml/h	No change	-7 ml/h	-14 ml/h
72≤	+13 ml/h	+6.5 ml/h	No change	-6.5 ml/h	-13 ml/h

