6.2 CRRT PARAMETERS

6.2.1 CITRATE ANTICOAGULATION

Each participating clinical site will use their regional citrate anticoagulation protocol. The clinical site is responsible to achieve and maintain a serum post filter ionized calcium level of <0.40 mmol/L throughout the entire SCD treatment period (day and night). The serum post filter ionized calcium level will be collected from the CRRT Circuit post SCD [REDACTED]. Examples of regional citrate anticoagulation protocols are included in Appendix D. If the site has difficulty in maintaining post-fiter iCa levels <0.4 mM from prior experience with patients in this body weight between 10 and 20 kg body weight, the Sponsor and Lead Investigator will discuss options of citrate protocols to be used in enrolled patients to meet post filter iCa levels <0.4 mM as required during SCD treatment.

See the RCA example protocol in Appendix D.

Clinical sites will utilize the following parameters to alleviate the metabolic derangements associated with regional citrate based anticoagulation:

- a) *Alkalosis:* Patients with an arterial pH <7.40 at enrollment will initiate CRRT with solutions containing either 25 or 35 meq/L of base as directed by local standard of care. During the study, if the patient's arterial pH increases to >7.45 OR the patient's serum bicarbonate increases to >35 meq/L, the CRRT solution will be changed to a base concentration of 25 meq/L, OR 0.9% NaCl will be added dialysis fluid to correct the alkalosis per local standard of care.
- b) *Citrate lock:* If the patient develops citrate lock, as defined by a serum ionCa <0.95 mmol/L and a total serum Ca >12.5 meq/L, the citrate infusion will be discontinued OR the CRRT clearance will be increased by 50% or per local standard of care, AND CRRT circuit Ca and patient Ca will be checked at least every one hour. For centers that stop citrate, once the patient ionCa is >1.0 mmol/L, the citrate will be restarted at a lower rate determined by the site investigator, and hourly ionCa pairs will be rechecked x 3 to ensure a stable patient ionCa >1 mmol/L and stable circuit ionCa <0.40 mmol/L.

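### Appendix D, Table 3: the step printed for calcium rates of 72 ml/h and over repeats a lower row and falls short of the table's own 20% / 10% headings

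*Combined protocol and SAP*

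**What the plan says.** Section 6.2.1 leaves the citrate method to the centers: "Each participating clinical site will use their regional citrate anticoagulation protocol". It offers Appendix D as an example that may be used. Appendix B lists the anticoagulation prescription as "Prescribed by Investigator Team – Treating Team".

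Appendix D holds two schemes.

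- **First scheme (item 2.a).** The citrate start rate is "Initial ACD-A™ rate = 1.5 x CRRT blood pump rate x min/hour", with the example that "if blood pump rate is 100 ml/minute; the ACD-A™ rate is 150 ml/hour". The calcium start rate is "Initial CaCl₂ rate = 0.6 x blood pump rate x min/hour", with the example that "if blood pump rate is 100 ml/minute; the CaCl₂ rate is 60 ml/hour".
- **Fixed-flow scheme.** This is offered to centers that miss their targets. Table 1 gives one setting for 10-20 kg: blood flow 21 ml/min, ACD-A 63 ml/h, calcium chloride 21 ml/h. Table 2 gives correction factors for the initial calcium rate. Table 3 gives the change in that rate from the patient's ionized calcium every 6 hours, in bands of current rate. Its outer columns are for 20% changes (the increase reads "Increase Rate +20%; notify ICU physician") and its inner columns for 10% changes.

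The last three rows of Table 3 print these steps:

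| Current rate (ml/h) | 20% columns (ml/h) | 10% columns (ml/h) |
|---|---|---|
| 62-<67 | ±13 | ±6.5 |
| 67-<72 | ±14 | ±7 |
| 72 and over | ±13 | ±6.5 |

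**The concern.** Down the table the step rises by 1 ml/h (20% columns) and 0.5 ml/h (10% columns) from each row to the next. At the last row it falls back, and all four values match those two rows above. A nurse following the printed row would change the rate by less than the heading promises, and the gap widens as the rate rises. It works in both directions: low calcium is corrected too slowly, and so is high calcium.

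The patients are children of 10 to 20 kg, and Table 3 is meant partly for those who sequester or release calcium or who accumulate citrate, whose rates may drift from the starting value. A printed infusion rule should agree with its own headings.

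**Working it through.** **Inputs.** Bands, steps and headings come from Table 3; blood flow 21 ml/min and calcium 21 ml/h from Table 1; the lowest and highest correction factors, 0.46 and 1.34, from Table 2. All are in Appendix D.

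**1. Reproduce the table's rule.** Divide each 20% step by 0.20 to find the rate at which it is exact.

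- <12: 2/0.20 = 10
- 12-<17: 3/0.20 = 15
- 17-<22: 4/0.20 = 20
- and so on in steps of 5, to 62-<67: 13/0.20 = 65, and 67-<72: 14/0.20 = 70

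In all 13 rows the result lies inside the row's own band. The 10% columns are half the 20% columns, so they give the same rates (for example 7/0.10 = 70).

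**2. Apply it to the last row.** 13/0.20 = 65 and 6.5/0.10 = 65 ml/h. This lies outside a band that begins at 72.

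**3. Share actually delivered.**

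| Rate (ml/h) | 20% would be | 13 ml/h is | 10% would be | 6.5 ml/h is |
|---|---|---|---|---|
| 72 | 14.4 | 18.1% | 7.2 | 9.0% |
| 78 | 15.6 | 16.7% | 7.8 | 8.3% |
| 85.1 | 17.0 | 15.3% | 8.5 | 7.6% |
| 100 | 20.0 | 13.0% | 10.0 | 6.5% |

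**4. Compare with the table's rounding.** The smallest share in any other row is at the top of the first: 2/12 = 16.7% and 1/12 = 8.3%. The row just before the last never drops below 14/72 = 19.4%. So from 72 to 78 ml/h the shortfall is no worse than rounding elsewhere in the table; above 78 ml/h it is larger than in any other row.

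**5. How often the row would be reached.** At 21 ml/min the initial rate runs from 21 × 0.46 = 9.7 to 21 × 1.34 = 28.1 ml/h. Following Table 3's own 20% increases:

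- from 28.1: 34.1, 41.1, 49.1, 59.1, 71.1, 85.1 (6 steps)
- from 21: 25, 30, 36, 43, 52, 63, 76 (7 steps)
- from 9.7: 11.7, 13.7, 16.7, 19.7, 23.7, 28.7, 34.7, 41.7, 49.7, 59.7, 71.7, 85.7 (12 steps)

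Each step needs a patient ionized calcium below 0.95 mmol/L. On the 6-hourly schedule, six such checks span 5 × 6 = 30 hours from first to last. This depends on the tabulated flow. If a team used Table 2 at a higher flow, the row could be the starting row from 72/1.34 = 53.7 ml/min (highest factor) or 72 ml/min (factor 1.00).

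**6. The starting-rate notation.** Taking minutes per hour as the unit of the coefficient, 1.5 min/h × 100 ml/min = 150 ml/h and 0.6 min/h × 100 ml/min = 60 ml/h. Both worked examples reproduce. Table 1 follows the same convention: 3 × 21 = 63 and 1 × 21 = 21.

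**The case against.** The strongest reply is that the row hardly matters, and most of that stands. The appendix is optional and the treating team prescribes. The column headings state the intended size, so a reader can see what was meant. At 72 ml/h the gap is 14.4 − 13 = 1.4 ml/h. Appendix D expects calcium to stay near goal from the initial rate. Section 6.2.1 requires circuit and patient calcium at least hourly (within 30 minutes) after any citrate or calcium rate change until targets are met, and sets a separate response to citrate lock. The first scheme has its own check: "Check patient and system ionized calcium one hour after any change in ACD-A™ or CaCl₂ rate". An undersized step would therefore be seen and repeated.

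A second reply is that 13 ml/h may be a deliberate ceiling. The documents do not exclude this. But no ceiling is stated, one set below the preceding row's 14 would be odd, and it would also limit decreases. A copied row is likelier, though not proven.

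A reader might also infer a second error, that the starting-rate formulas call for 60 times the intended dose. The documents do not support that. No 60 is printed. Putting one in would give 1.5 × 100 × 60 = 9,000 ml/h of citrate against a blood flow of 100 × 60 = 6,000 ml/h, an obvious absurdity. The examples on the same lines fix the dose. The notation is ambiguous, not a dosing error.

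**Conclusion.** The last row of Table 3 does not follow its own headings and should be corrected or explained. The shortfall is small where the row begins and exceeds the table's ordinary rounding only above 78 ml/h. The priority is the lowest: at the tabulated 21 ml/min at least six consecutive maximum increases are needed, each notifying the ICU physician.

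This rests on two assumptions: that the headings state the intended rule, and that centers using the fixed-flow scheme keep to the Table 1 blood flow. Nothing here supports an inference that a child is likely to be misdosed, or that any endpoint, sample size or analysis is affected.

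**What to change.** The clinical lead should confirm what was intended for 72 ml/h and over. Unless a cap was meant, replace the fixed steps with 20% and 10% of the current rate. If a cap was meant, print it as a cap and say whether it applies to decreases as well.

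Continuing the pattern with a fixed ±15 / ±7.5 would mend only the start of an open-ended band: 15/72 = 20.8%, but 15/100 = 15%. A percentage is safer.

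On the same reissue, the units in item 2.a could be made plain: ACD-A in ml/h equals 1.5 times the blood pump rate in ml/min, and calcium chloride in ml/h equals 0.6 times that rate. This is a clarification only.

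The cost is corrected Appendix D pages, sent also to any center already using the example. It adds no procedure, data item or analysis.
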